University of Kansas Medical Center RESEARCH PROTOCOL INVOLVING HUMAN SUBJECTS TEMPLATE WITH GUIDANCE

Version date: 8/11/2015

Principal Investigator: [name].

Study Title: Impact of Rifaximin Therapy on Intestinal Byproducts in Chronic Kidney Disease

Co- Investigator(s): [name], D.O.

[name], M.B., BChir [name]. [name] [name] [name]

(NOTE: not all sections of this template will apply to all projects. "N/A" is an acceptable response.)

I. Purpose, Background and Rationale

A. Aim and Hypotheses

1. Begin with a brief introduction to describe the origin and importance of the study.

Trimethylamine-N-oxide (TMAO) is a circulating organic compound produced by the metabolism of dietary L-carnitine and choline. TMAO was recently identified to directly induce atherosclerosis in rodents and is strongly associated with the incidence of cardiovascular events in humans. The proposed investigation is a prospective pilot study to assess the impact of alterations in the intestinal flora by short-term antibiotic suppression (with Rifaximin) and to measure its effect on serum TMAO levels in patients with advanced-stage (stage IV-V) chronic kidney disease.

2. Clearly state the aim(s) and hypothesis(es), listing them by number if there is more than one.

Hypothesis: Treatment of CKD patients with Rifaximin will suppress the bacterial flora that are responsible for the generation of trimethylamine, a TMAO precursor, and subsequently reduce serum TMAO concentrations.

Primary Aim:

 The primary outcome of interest will be the change in serum TMAO concentrations (post-therapy minus pre-therapy TMAO) following Rifaximin administration for 10 days.

Secondary Aims:

- 1. To measure the change in urine TMAO
- 2. To measure the change in serum endotoxin, IL-6, IL-8, TNF-alpha levels
- 3. To measure the alteration of bowel microbiota
- 4. To assess the above changes in steady state, 2 weeks after completion of therapy

B. Background and Significance

1. Study Significance: what the proposed research is intended to accomplish and the importance of the results

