The proposed investigation is a prospective pilot study to assess the impact of alterations in the intestinal flora by short-term antibiotic suppression (with Rifaximin) and to measure its effect on serum TMAO levels in patients with advanced-stage (stage IV-V) chronic kidney disease. Results may lead to future investigations to better understand how alterations in TMAO metabolism may impact cardiovascular outcomes in patients with chronic kidney disease.

2. Describe the facts, events, and thought processes leading to the currently proposed research project.

We previously postulated that TMAO levels would be substantially elevated in patients with CKD, and to test this hypothesis we performed a cross-sectional analysis of serum TMAO concentrations in a cohort of patients with varying levels of CKD and normal healthy controls. In this study, we observed serum TMAO concentrations progressively rise in CKD. We seek to determine if circulating concentrations of TMAO can be reduced by alterations to the gut flora.

3. Literature Review: Summarize any pertinent studies supporting this proposed project. Human studies are preferred; include animal studies only if human data are lacking.

Wang Z., et al. Gut Flora Metabolism of Phosphatidylcholine and Cardiovascular Risk. *Nature* 2011.

- Dietary supplementation of mice with choline, TMAO or betaine promoted upregulation of multiple macrophage scavenger receptors linked to atherosclerosis, and supplementation of mice with choline or TMAO promoted atherosclerosis.
- Suppression of enteric microflora in atherosclerosis-prone mice inhibited dietary choline enhanced atherosclerosis.
- Prognostic value for the risk of CVD was determined in humans by measuring fasting levels of TMAO and determining its association with prevalent vascular events, including peripheral vascular disease, coronary artery disease and myocardial infarction.
- In atherosclerosis prone mice supplementation with choline was shown to increase aortic atherosclerosis when compared to atherosclerosis prone mice on a normal chow diet.

Koeth RA, et al. Intestinal Microbiota Metabolism of L-carnitine, a nutrient in red meat, promotes atherosclerosis. *Nature Medicine* 2013

- They revealed that subjects with elevated L-carnitine, if also found to have elevated TMAO, had increased prevalence of cardiovascular disease and higher incidence of major adverse cardiovascular events (MI, stroke or death).

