in rodents and was found to be strongly associated with the incidence of cardiovascular events in humans (2-5). In normal physiologic conditions, circulating TMAO is rapidly removed from circulation primarily by excretion into the urine (7). We previously postulated that TMAO levels would be substantially elevated in patients with CKD, and to test this hypothesis we performed a cross-sectional analysis of serum TMAO concentrations in a cohort of patients with varying levels of CKD and normal healthy controls. In this study, we observed serum TMAO concentrations become markedly elevated in the advanced stages of CKD, with end-stage renal disease (ESRD) patients exhibiting mean levels 30-fold higher than healthy controls.

If TMAO contributes to atherosclerosis formation in CKD patients, therapeutic interventions to reduce TMAO production may represent a method to reduce cardiovascular morbidity and mortality in this population. Prior studies suggest that short-term suppression of gut flora with antibiotics dramatically decreased TMAO levels in patients with normal kidney function (5); however, this approach has not yet been tested in patients with CKD that exhibit much higher serum levels of TMAO.

Rifaximin is a novel antibiotic that is currently approved for treatment of hepatic encephalopathy in patients with end-stage liver disease. Rifaximin demonstrates little systemic absorption, with 97% of the parent drug being excreted unchanged in the feces (9). Its primary use is to target pathogenic intestinal bacteria in various disease states , including cirrhosis and traveler's diarrhea. In this study we seek to evaluate whether Rifaximin will decrease levels of TMAO in patients with advanced kidney disease and to study the effects of Rifaximin on the intestinal microbiome of patients with CKD.

Explain how the performance of this proposed project will advance our knowledge in this field, and/or improve our understanding of the disease or physiological condition being studied.

This study will determine if elevated levels of TMAO in CKD are at least partially dependent on the presence of certain intestinal flora and if serum TMAO levels are modifiable by therapy with Rifaximin.

3. Explain how this study might improve the diagnosis or treatment of the disease being studied (if applicable), or advance knowledge in the field.

This will provide preliminary evidence to support the intestinal flora as a target for reducing TMAO levels in CKD patients.

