Blinding will be involved in this study. The primary investigator, study participants, and team members involved in serum/urine end point analyses will be blinded to treatment arm. The investigational pharmacy is responsible for study group assignment and is not blinded. The study team member involved in the fecal bacterial genome analysis will not be blinded, as knowledge of treatment arm will be necessary for the accurate assessment of changes in fecal microbiome composition among study participants.

3. State the maximum number of subjects to be enrolled in each group. Include power calculations to explain what can be studied with the proposed sample size and specify the statistical tests that will be used to test **each** hypothesis. If the research project needs to be pilot tested, state how many subjects will be enrolled in the pilot test and how the procedures for the pilot test will differ from those used in the research protocol.

There will be a total of 30 subjects enrolled; 15 participants will receive Rifaxmin and 15 will receive placebo.

D. Subject Criteria (See Vulnerable Populations appendix, if applicable): Include age range, gender, disease, and stage of treatment. Justify excluding subjects based on race or

gender (including child-bearing potential for women), age (children), or non-English speakers.

- 1. Inclusion criteria: State the criteria for inclusion in the study in a specific and detailed manner.
 - Patients 18 years of age or older
 - Stage IV-V chronic kidney disease (eGFR ≤ 39 ml/min/1.73m²)
- 2. Exclusion criteria: State the criteria for excluding potential subjects from the study in a specific and detailed manner.
 - Patients with normal renal function or those with less advanced kidney disease
 - Inability or unwillingness to provide consent
 - Patients undergoing hemodialysis or peritoneal dialysis therapy or those who have undergone organ transplant
 - Patients who may be pregnant
 - Hemodynamically unstable patients
 - Patients with liver failure, pancreatic insufficiency, or inflammatory bowel disease
 - Patients with ongoing or recent infection and those with history of C-diff infection
 - Patients with abnormal bowel structure secondary to surgical or anatomic variations
 - Patients on certain medications including immunosuppressants, antidiarrheal agents, and current or recent (within the last 2 months) use of antibiotics

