4. Attach a copy of the recruitment letter or introductory statement and describe planned use or distribution of the document.

There will not be a recruitment letter.

B. Screening Interview/questionnaire: If an interview or questionnaire will be used for screening, attach a copy and indicate where, how, and who will conduct the interviews and their qualifications. Address how consent to participate in the screening process will be obtained.

Clinic patients will be screened for inclusion and exclusion criteria. If they are appropriate for inclusion in the study they will be approached by their clinical nephrology team members who will assess their interest and willingness to participate in the study. If they are interested in participation a member of the study team will discuss the study in further detail.

C. Informed consent process and timing of obtaining of consent

1 Indicate who will give subjects detailed and comprehensive information about the study and obtain their written consent.

A member of the study team as outlined above.

2 Indicate how the consenting process will be structured to ensure independent and thoughtful decision-making, and what steps will be taken to avoid coercion and guarantee confidentiality.

Clinic patients will be screened in advance for inclusion and exclusion criteria. During their clinic visit with their clinical nephrologist, their doctor will ask if they are interested in participating in the study. If the patient expresses interest, a member of the study team will discuss the project with the patient. The consent may be obtained at that clinical visit if time permits for full explanation and patient is agreeable. Alternatively they may take the consent form home for review and a study visit will be arranged at a separate time and location.

Indicate how, and by whom, it will be determined whether the subject is able to give informed consent, or whether their legal guardian will give informed consent. For subjects whose ability to give informed consent may be compromised by cognitive and/or decisional impairment (examples may include individuals with a psychiatric disorder, an organic impairment, a developmental disorder, or those suffering from a terminal illness, degenerative disease, severe physical handicap or dependence on drugs or alcohol), complete Appendix I.

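### Does the eGFR limit of 39 in the inclusion criteria contradict the stage IV-V label beside it?

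*Combined protocol and SAP*

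**What the plan says.** Everything on this point is in the combined protocol and SAP.

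- **Section II.D.1, inclusion:** patients aged 18 or over with "Stage IV-V chronic kidney disease (eGFR ≤ 39 ml/min" per 1.73 m². This is the only eGFR value in the document.
- **Section II.D.2, exclusion:** "Patients with normal renal function or those with less advanced kidney disease", with no number attached.
- **Sections I.A.1 and I.B.1:** the same sentence appears in both and gives the purpose as to "measure its effect on serum TMAO levels in patients with advanced-stage (stage IV-V) chronic kidney disease", without an eGFR range.
- **Section I.C.1:** the aim is to "evaluate whether Rifaximin will decrease levels of TMAO in patients with advanced kidney disease". It names neither a stage nor a number.
- **Section III.C.2:** "Clinic patients will be screened in advance for inclusion and exclusion criteria", so the limit acts before a patient is approached.

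Apart from the parenthesis in II.D.1, nothing says which eGFR values make up stage IV or stage V.

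**The concern.** A reader who assumes that stage IV begins below 30 sees a label and a number that disagree. A patient with an eGFR of 35 would pass the number and fail the label. The same patient might also be caught by the exclusion of less advanced disease, which has no figure to settle it.

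Two things would be at stake. First, screeners might apply the criterion differently, and section II.D.3 allows participation to be ended if a patient is later found not to meet the criteria. Second, a conclusion worded for stage IV-V disease might cover a sample that includes milder disease. The protocol's own cross-sectional data (section I.B.3) show serum TMAO rising with CKD severity, so the severity range studied matters to a reader.

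**Working it through.** **Is there a figure to reproduce?** The limit of 39 is a stated criterion, not a derived quantity, so no formula yields it. The check is whether anything else in the document conflicts with it.

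**Step 1: the texts side by side.**

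| Place | Population wording | eGFR figure |
|---|---|---|
| I.A.1 and I.B.1 | advanced-stage, stage IV-V | none |
| I.C.1 | advanced kidney disease | none |
| II.D.1 | stage IV-V | ≤ 39 |
| II.D.2 | excludes less advanced disease | none |

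No second number competes with 39. A label followed by a number in parentheses is the usual form of an operational definition. Read that way, less advanced disease in II.D.2 means an eGFR above 39, and the two lists give one rule.

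**Step 2: size of the mismatch under an assumed boundary.** Suppose stage IV means eGFR below b, where b is an assumption because the document gives none. The whole-number values that meet the limit but not the label number max(0, 39 − b + 1).

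| Assumed b | Calculation | Values in the band |
|---|---|---|
| 30 | 39 − 30 + 1 | 10 (30 to 39) |
| 35 | 39 − 35 + 1 | 5 (35 to 39) |
| 39 | 39 − 39 + 1 | 1 (39) |
| 40 | 39 − 40 + 1 | 0 |

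These count eGFR values, not patients. Turning them into patients needs the eGFR distribution in the recruiting clinics, which the document does not give. The number of affected patients among the 30 could be zero.

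**Step 3: does the limit touch the statistics?** Section II.C.1 uses a mean change of −30%, a standard deviation of 30%, 90% power and a type I error of 0.05; section V.A specifies a two-sided paired t-test. The standardised change is 30/30 = 1, so the noncentrality is √n. Exact noncentral-t power is 0.883 at n = 12 and 0.911 at n = 13. Thus 13 is the smallest sample reaching 90%, as the protocol states. eGFR is not an input to this calculation or to the test. Both arms are drawn under the same criterion, so the limit cannot bias the randomised comparison.

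**The case for a change.** The best case for a change is that clarification is cheap and the template asks for specific criteria. One line in II.D.1 could state the stage definition, and the exclusion could carry the same number. With only 30 patients, eligibility should not rest on interpretation, particularly when II.D.3 allows removal after enrolment. Severity is related to TMAO level in the protocol's own data, so the population should be named accurately. The figure also occurs only once, so a digit misread in conversion from PDF cannot be excluded.

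Part of this stands. The stage definition could have been spelled out, and under the assumption of 30 the label would be loose. The rest does not amount to a fault in the plan:

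- Nothing inside the document makes 39 look wrong. The doubt comes from a boundary brought in from outside.
- A screener who follows the text already has one numeric limit.
- A conversion error would not be an error in the plan, and there is no positive sign of one.
- A conclusion about stage IV-V would misdescribe the sample only to the extent that patients in the assumed band enrol. The hypothesis in I.A.2 concerns CKD patients, and the primary objective in II.A names no stage, so the main inference does not hang on the label.

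**Conclusion.** No change is needed. The observation is correct only as a conditional: if stage IV begins below 30, the limit admits eGFR 30 to 39; if it begins below 40, there is no discrepancy. The document does not establish either boundary, and it supplies one usable rule.

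The effect on sample size, power, the primary test and the randomised comparison is nil. The effect on the description of the population ranges from none to a slightly loose label, and the number of patients concerned cannot be estimated. Patients' eGFR must be known in order to apply the criterion, so a report can state the limit used and the values observed. Analysts would do this as a matter of course, and it removes any ambiguity in the label. Checking the digit against the source, or adding the staging definition at the next routine revision, would be editorial tidying.

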- 3. Withdrawal/Termination criteria: Include the specific circumstances in which the subject's participation will be terminated by the investigator. Include any necessary safety precautions to be applied to those who withdraw (tapering drug doses, evaluative x-ray, etc.)
 - Participation may be terminated if subject is found to not meet the inclusion or exclusion criteria. Participants may withdraw at any time.
- 4. Clarify whether a study subject may participate in another research study while participating in this research study.
 - Patients should not participate in another research study while taking the study medication but exceptions may be made dependent on the nature of the other research study.

E. Specific methods and techniques used throughout the study

1. Laboratory tests: Methods for collecting specimens and data. Indicate purpose, amount and timing of tests performed (e.g., blood tests, urine tests, CSF tests, EKGs, etc.). Include specific test components and estimated volume and type of specimens needed for each test.

Serum and urine samples (30ml each) will be collected at the baseline and post-therapy visits (day 0, day 11, and day 25) for measurement of TMAO, endotoxin, IL-6, IL-8, and TNFa levels. Fecal specimens will be collected at these same time points in order to assess changes in the intestinal microbiome after administration of Rifaximin.

2. Study Procedures: Describe each procedure to be used in the study, including the instruments used, time required for each procedure, cognitive assessments, etc.

Blood, urine and stool samples will be collected for analysis. Aside from venipuncture there will be no other procedures.

3. Clearly indicate which procedures, tests, visits, etc., are parts of usual standard therapy and which are performed solely for research purposes. Make it clear which tests are routinely performed for clinical care but are providing data for the research (and are billable to insurance companies), and which tests are only performed for research purposes (not billable to insurance companies).

Any samples collected during the specified research appointments will be used for research purposes only and will not be billed.

4. Describe the fate of any body component (blood, CSF, bone marrow, etc.) used in the study, emphasizing confidentiality of labeling of the sample and the sample's destruction or storage.

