Blood, urine and stool samples will be labeled with study information and by the subjects' unique study ID. They will be analyzed in the lab of [name] and the lab of [name] at the University of Pittsburgh Medical Center. Additional serum and urine samples will be stored in a -80°C freezer in [name] lab for those patients consenting for sample storage.

5. Timeline: Consider attaching a study flow chart illustrating subject visits and tests or procedures to be performed at each visit **and/or** include a chart or graph format that reflects the project activities and anticipated time frame of completion.

Day 0 (baseline visit): Consented participants will have an initial appointment dedicated to the collection of baseline samples and study medication will be dispensed at this visit. Complete review of the patient's history and physical examination will be recorded. All study participants will continue receive standard of care treatment for their chronic kidney disease. Study participants will be provided with a 10-day course of Rifaximin. A medical history will be obtained, including current medications, comorbid conditions, lifestyle indicators (such as tobacco and alcohol use), review of recent laboratory studies (such as BMP, CBC, and lipids); this information will be recorded and stored on all study participants. Serum, urine and fecal samples will be collected at this

visit. On Day 1, study participants will begin Rifaximin 550mg PO BID or placebo for a total of ten days duration.

Day 11 (post-therapy follow-up visit): Study participants will provide stool samples within 24 hours of their last dose of Rifaximin or placebo. Serum and urine samples will be drawn at this study visit. Vital signs will be checked and a brief interview will be conducted to assess for any potential adverse reactions to the study medication. Follow up visits can be arranged at the patient's request if needed.

Day 25 (steady state follow-up visit): Study participants will provide stool samples. Serum and urine samples will be drawn at this study visit. Vital signs will be checked and a brief interview will be conducted to assess any recent health changes.

- **F. Risk/benefit assessment:** As appropriate, address the following parameters as each relates to the individual subject in the study. Be sure to include consideration of study assignment (Arm A, Arm B, placebo, active substance, etc):

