APPENDIX I: VULNERABLE POPULATIONS

I. If the recruitment plan includes any of the groups noted below, explain how they will be protected and how consent will be obtained. In general, regulations allow subjects identified as part of vulnerable populations to be included if the research cannot be accomplished without their involvement.

This study will not involve vulnerable populations.

II. Cognitively or decisionally impaired individuals: These populations include those with a psychiatric disorder, an organic impairment, a developmental disorder, and those with a terminal illness, degenerative disease, severe physical handicap or dependence on drugs or alcohol. The protocol should explain how the appropriate surrogate decision-maker will be identified, in accordance with Kansas state law. Recruitment procedures and materials, and consenting procedures and documents must be submitted.

This study will not involve subjects who are unable to consent for themselves including cognitively impaired subjects.

III. Children: Consenting procedures, assent and consent forms must be submitted. Recruitment procedures and materials are also required. Consideration and procedures for re-consent will be required if the minor will attain age 18 years while in the study.

This study will not include anyone under the age of 18.

- **IV. Pregnant women:** Federal regulations require that inclusion of pregnant women must be justified by scientific rationale and based upon animal studies when applicable. Please refer to the IRB website for a fact sheet about including pregnant women and fetuses in research. This study will not include pregnant subjects.
- **V. Prisoners:** Research involving prisoners requires specific justification and also requires review by an IRB that includes a prisoner representative. Please consult with the IRB office prior to proposing a prisoner population for your research.

This study will not involve incarcerated individuals.

- **VI. Students and/or Employees**: to reduce potential coercion or interference with normal job duties, if students or employees are to be recruited as subjects of human research:
 - **A.** For research involving KUMC students, include a letter of support from the Dean of the School.

Students will not be sought for inclusion in this study.

B. For research that specifically targets KUMC employees, explain [see SOP 9]

Employees will not specifically be sought for inclusion in this study.

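### Pregnancy is an exclusion, but no objective check for it is planned before study medication is dispensed

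*Combined protocol and SAP*

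**What the plan says.** **Exclusion.** II.D.2 excludes "Patients who may be pregnant". The consent section (III.C) says that pregnant patients will not be involved, and Appendix I, item IV, states "This study will not include pregnant subjects". None of the three gives a method.

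**Population.** II.D.1 admits "Patients 18 years of age or older". There is no upper age limit, no restriction by sex, and no criterion on childbearing potential or contraception. Childbearing potential appears only in the template's prompt at the head of II.D.

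**Tests and procedures.** II.E.1 collects serum and urine on Days 0, 11 and 25 "for measurement of TMAO, endotoxin, IL-6, IL-8, and TNFa levels"; stool is for the microbiome. II.E.2 adds "Aside from venipuncture there will be no other procedures". Under II.E.3, "Any samples collected during the specified research appointments will be used for research purposes only". Under II.E.4, "Additional serum and urine samples will be stored in a -80°C freezer" where the patient has consented to storage.

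**Sequence.** By the timeline in II.E.5, Day 0 comprises history, physical examination, review of recent laboratory results, sampling and dispensing. Dosing starts on Day 1 and lasts ten days.

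**The concern.** The sponsor chose to keep pregnant patients out and worded the criterion cautiously, covering possible as well as confirmed pregnancy. As the plan is written, a site can apply it only from the chart, by examination or by asking. Those routes depend on someone already knowing or suspecting that the patient is pregnant. An early pregnancy that nobody has recognised passes every written step.

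The stake is participant safety and the integrity of an eligibility criterion; the primary analysis is not affected. II.F.5 says that individuals are not expected to benefit directly, so no personal benefit offsets an exposure that the plan itself meant to avoid.

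**Working it through.** There is no figure to reproduce. The check is whether any written step, taken in order, would detect an unrecognised pregnancy before the first dose.

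1. **Clinic screening (III.B).** Patients are screened against the criteria in clinic. No test is named. A pregnancy on record or reported by the patient would be found; an unrecognised one would not.
2. **Day 0 history and examination (II.E.5).** Medications, comorbid conditions and lifestyle factors are listed. Menstrual status, contraception and pregnancy are not. A suspected pregnancy may come to light, but asking cannot reveal what the patient does not know.
3. **Day 0 review of existing results (II.E.5).** The examples are BMP, CBC and lipids. The list is open-ended, so a recent pregnancy test would be seen if one happened to exist, but nothing calls for one.
4. **Day 0 serum and urine (II.E.1, II.E.4, IV.B).** The stated uses are TMAO, endotoxin, IL-6, IL-8, TNF-alpha and optional storage. Pregnancy tests planned: 0.
5. **Assignment and dispensing (II.C.2, II.E.5).** The investigational pharmacy assigns the group, at a time that the plan does not state. Dispensing takes place at the Day 0 visit and depends on no pregnancy result.
6. **After dosing starts (II.D.3, II.E.5).** Participation may be ended if a criterion is found not to be met, but no procedure is planned that would find a pregnancy. The next visit, Day 11, falls after the ten-day course and consists of samples, vital signs and an interview about adverse reactions.

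Steps 1 to 3 protect against known or suspected pregnancy. No step protects against an unrecognised one.

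**Size.** The number affected would be 30 × (share of childbearing potential) × (share of those with an unrecognised pregnancy at Day 0). The documents give neither share. Under 1:1 allocation, 15 of 30, or half, receive rifaximin, so an affected participant has a one-in-two chance of exposure to it. No numerical estimate is justified beyond that. The second share should be small, which makes the product very small.

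**The case against.** **The criterion can be applied clinically.** Possible pregnancy is a broad test that a careful clinician can apply from history. This stands in part: a reader might infer that the exclusion cannot be applied at all, and the screening and Day 0 assessments show otherwise. The gap is confined to unrecognised pregnancy.

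**The sentence on procedures is not a full inventory.** II.E.5 schedules a physical examination and vital signs, which II.E.2 also leaves out. That is fair, so the point should not rest on II.E.2 alone. It rests on II.E.1, where the template asks for specific test components and the answer names none for pregnancy.

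**Appendix I is a declaration of scope.** It answers a template question about which vulnerable groups are in the recruitment plan. A reader might infer a false assurance or a contradiction with II.D.2. The documents do not support that; the two statements agree, and what both lack is a method.

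**Harm is not shown.** The rationale (I.C) describes little systemic absorption, and the risk section (II.F.1) lists no reproductive risk. A reader might infer a demonstrated fetal hazard; nothing in the documents establishes one. Equally, the documents do not use low absorption to justify omitting a check, and the sponsor kept the exclusion.

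**Other exclusions also lack a named test.** Liver failure and pancreatic insufficiency are examples. Those conditions are more likely to be known to the treating clinic, whereas an early pregnancy may be unknown to patient and clinician alike.

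**The provision may be in text not seen here.** The consent pages and a short part of section II, just before the data and safety monitoring plan, were not available. This lowers confidence somewhat. The sections where a test would normally appear are all present and silent.

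**Conclusion.** The point holds in a limited form. The plan excludes possible pregnancy but provides no objective means of ascertaining it before dispensing, so a site following the plan exactly could enrol a patient with an unrecognised pregnancy and, if she is allocated to rifaximin, expose her for 10 days.

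The number affected cannot be derived from the documents. A reader might be tempted to assume a share of childbearing potential and multiply by 30. That share has no basis in the documents, and the result would count people who could become pregnant, not pregnancies. Nor would every affected participant be exposed to rifaximin, since half receive placebo.

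The conclusion assumes that at least some participants can become pregnant, which the eligibility criteria allow, and that no pregnancy test is specified in the text that was not available. The change is worth making because it enforces the sponsor's own criterion at almost no cost, even though few participants, or none, may be affected.

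**What to change.** Keep the exclusion criterion as it is, and make these changes:

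- **II.D:** define childbearing potential for this study.
- **II.E.1 and the Day 0 entry in II.E.5:** for participants who meet that definition, add a urine pregnancy test on the urine already collected at Day 0. Require the result before the pharmacy assigns treatment and before dispensing, and apply the existing exclusion if it is positive.
- **II.C.2 or II.E.5:** state when the pharmacy makes the assignment, so that this order can be followed.
- **II.E.2:** amend the sentence on other procedures so that it agrees with the added test.

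II.E.3 can stay as written, because an eligibility test is a research use of the sample and would not be billed.

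The cost is a few test strips, a few lines of protocol text and a short delay before dispensing. No extra visit or sample is needed. A single Day 0 test reduces the chance of missing a very early pregnancy without removing it, and it cannot detect conception during the dosing period.
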